14.8 PREMATURE DISCONTINUATION OF THE STUDY OR PREMATURE CLOSE-OUT OF A SITE

14.8.1 By the Sponsor

The Sponsor has the right to terminate the participation of either an individual site or the study at any time, for any reason, including but not limited to the following:

- The information on the product leads to doubt as to the benefit/risk ratio;
- Patient enrollment is unsatisfactory;
- The Investigator has received from the Sponsor all IMP, means and information necessary to perform the clinical trial and has not included any patient after a reasonable period of time mutually agreed upon;
- Non-compliance of the Investigator or Subinvestigator, delegated staff with any provision of the clinical trial protocol, and breach of the applicable laws and regulations or breach of the ICH GCP;
- The total number of patients are included earlier than expected;

In any case the Sponsor will notify the Investigator of its decision by written notice.

14.8.2 By the Investigator

The Investigator may terminate his/her participation upon thirty (30) days' prior written notice if the study site or the Investigator for any reason becomes unable to perform or complete the clinical trial.

In the event of premature discontinuation of the study or premature close-out of a site, for any reason whatsoever, the appropriate IRB/IEC and regulatory authorities should be informed according to applicable regulatory requirements.

14.9 CLINICAL TRIAL RESULTS

The Sponsor will be responsible for preparing a clinical study report and to provide a summary of study results to the Investigator.

14.10 PUBLICATIONS AND COMMUNICATIONS

The Investigator undertakes not to make any publication or release pertaining to the study and/or results of the study prior to the Sponsor's written consent, being understood that the Sponsor will not unreasonably withhold its approval.

As the study is being conducted at multiple sites, the Sponsor agrees that, consistent with scientific standards, a primary presentation or publication of the study results based on global study outcomes shall be sought. However, if no multicenter publication is submitted, underway or planned within twelve (12) months of the completion of this study at all sites, the Investigator shall have the right to publish or present independently the results of this study in agreement with other Investigators and stakeholders. The Investigator shall provide the Sponsor with a copy of any such presentation or publication for review and comment at least 30 days in advance of any presentation or submission for publication. In addition, if requested by the Sponsor, any presentation or submission for publication shall be delayed for a limited time, not to exceed 90 days, to allow for filing of a patent application or such other justified measures as the Sponsor deems appropriate to establish and preserve its proprietary rights.

The Investigator shall not use the name(s) of the Sponsor and/or its employees in advertising or promotional material or publication without the prior written consent of the Sponsor. The Sponsor shall not use the name(s) of the Investigator and/or the collaborators in advertising or promotional material or publication without having received his/her and/or their prior written consent(s).

The Sponsor has the right at any time to publish the results of the study.

15 CLINICAL TRIAL PROTOCOL AMENDMENTS

All appendices attached hereto and referred to herein are made part of this clinical trial protocol.

The Investigator should not implement any deviation from, or changes of the clinical trial protocol without agreement by the Sponsor and prior review and documented approval/favorable opinion from the IRB/IEC of an amendment, except where necessary to eliminate an immediate hazard(s) to clinical trial patients, or when the change(s) involves only logistical or administrative aspects of the trial. Any change agreed upon will be recorded in writing, the written amendment will be signed by the Investigator and by the Sponsor and the signed amendment will be filed with this clinical trial protocol.

Any amendment to the clinical trial protocol requires written approval/favorable opinion by the IRB/IEC prior to its implementation, unless there are overriding safety reasons.

In some instances, an amendment may require a change to the informed consent form. The Investigator must receive an IRB/IEC approval/favorable opinion concerning the revised informed consent form prior to implementation of the change and patient signature should be re-collected if necessary.

[figure not shown]

17 APPENDICES

Appendix A Guidance for the follow-up of laboratory abnormalities by Sanofi

[figure not shown]
Note

- The procedures described in the above flowchart are to be discussed with the patient only in case the event occurs. If applicable (according to local regulations), an additional consent (e.g., for HIV testing) will only be obtained in the case the event actually occurs.
- For individuals of African descent, the relevant value of concern is <1000/mm³

Neutropenia are to be recorded as AE only if they are :

- Symptomatic, and/or
- Requiring either corrective treatment or consultation, and/or
- Leading to IMP discontinuation or modification of dosing, and/or
- Fulfilling a seriousness criterion [in that case, the event (SAE) should be notified within 24 hours to the MTI], and/or
- Defined as an Adverse Event of Special Interest (AESI) with immediate notification

THROMBOCYTOPENIA

[figure not shown]

Note:

The procedures above flowchart are to be discussed with the patient only in case described in the event occurs. If applicable (according to local regulations), an additional consent (e.g., for HIV testing) will only be obtained in the case the event actually occurs.

[figure not shown]
Thrombocytopenia is to be recorded as AE only if at least one of the criteria listed in Section 10.4.3 is met

INCREASE IN ALT

NOTE: ALT \geq 3 ULN (IF BASELINE ALT < ULN) OR ALT \geq 2 TIMES THE BASELINE VALUE (IF BASELINE ALT \geq ULN) SHOULD BE NOTIFIED WITHIN 24 HOURS TO THE MONITORING TEAM (SEE SECTIONS 10.4.1.3 AND 10.4.5). IN ADDITION, IF ALT $<$ 3 ULN MEETS A SERIOUSNESS CRITERION, THE EVENT SHOULD BE NOTIFIED WITHIN 24 HOURS TO THE MONITORING TEAM

SUSPICION OF RHABDOMYOLYSIS

Suspicion of rhabdomyolysis is to be recorded as AE only if at least one of the criteria listed in Section 10.4.3 is met

EFC14011 Amended Protocol02

ELECTRONIC SIGNATURES

Signed by	Meaning of Signature	Server Date (dd-MMM-yyyy HH:mm)
	Clinical Approval	
	Regulatory Approval	
	Clinical Approval

## LIST OF ABBREVIATIONS AND DEFINITION OF TERMS

AE:	adverse event
AESI:	adverse event of special interest
ALT:	alanine aminotransferase
ATC:	anatomic category
BP:	blood pressure
CKD:	Chronic Kidney Disease
DBTP:	double blind treatment period
eCRF:	electronic case report form
HLGT:	high level group term
HLT:	high level term
HR:	heart rate
IMP:	investigational medicinal product
iPTH:	intact parathyroid hormone
IVRS:	interactive voice response system
IWRS:	interactive web response system
LDL-C:	low density lipoprotein cholesterol
LLT:	Low level term
LOCF:	last observation carried forward
MedDRA:	Medical Dictionary for Regulatory Activities
mITT:	modified Intent To Treat
PCSA:	potentially clinically significant abnormality
PT:	preferred term
Q1:	first quartile
Q3:	third quartile
SAE:	serious adverse event
SD:	standard deviation
SOC:	system organ class
TEAE:	treatment emergent adverse event
TID:	3 times per day

## 1 OVERVIEW AND INVESTIGATIONAL PLAN

### 1.1 STUDY DESIGN AND RANDOMIZATION

This is a phase III, multi-center, randomized, double blind, placebo-controlled, balanced (1:1, Renvela: placebo), parallel-group study to evaluate the efficacy and safety of Renvela versus placebo in hyperphosphatemic CKD patients not on dialysis in China.

Eligible patients who are taking a phosphate binder at screening visit will enter a 2-week phosphate binder washout period. Eligible patients who are not taking a phosphate binder at screening visit will proceed directly to the start of the 8-week treatment period (Day 1).

Randomization will be stratified according to baseline serum phosphorus ( $\geq 5.5 - 6.0$  mg/dL [ $1.78 - 1.94$  mmol/L] and  $>6.0$  mg/dL [ $1.94$  mmol/L]). After randomization, patients will receive double-blind study treatment (either Renvela or placebo) over a period of 8 weeks.

Patients will be followed for 2 weeks after the last visit of the Double Blinded Treatment Period (DBTP).

### 1.2 OBJECTIVES

#### 1.2.1 Primary objectives

The primary objective of this study is to demonstrate efficacy of Renvela tablets in the reduction of serum phosphorus in hyperphosphatemia in patients with CKD not on dialysis.

#### 1.2.2 Secondary objectives

The secondary objectives are:

- To document the efficacy of Renvela tablets in the reduction of serum lipids (total cholesterol and low-density lipoprotein cholesterol [LDL-C]).
- To document the efficacy of Renvela tablets in the reduction of calcium-phosphorus product.
- To document the efficacy of Renvela tablets in the reduction of iPTH.
- To document the efficacy of Renvela tablets in proportion of patients reaching the target serum phosphorus level (4.6 mg/dL [1.49 mmol/L], inclusive).
- To evaluate safety of Renvela tablets.

### 1.3 DETERMINATION OF SAMPLE SIZE

The sample size calculations are based on the primary efficacy variable of serum phosphorus change from baseline to Week 8, with the following assumptions:

- A common standard deviation (SD) of 2 mg/dL, which is assumed based on the data from previous trials
- A 1 mg/dL mean difference between test and placebo in change from baseline in serum phosphorus
- A t-test at a 2-sided 5% significance level with 90% power
- Expected dropout rate = 15%.

Based on the above assumptions, 101 patients per arm are needed for this study. Calculations were made using nQuery Advisor 7.0.

## 1.4 STUDY PLAN

The following figure presents the graphical study design:

V1  
Screening  
Visit

- R=Randomization
- Screening criteria:
  - CKD patients not on dialysis
  - Serum phosphorus level  $\geq 5.5$  mg/dL (1.78 mmol/L)
- Stratification factor, at the time of randomization, is screening serum phosphorus ( $\geq 5.5 - 6.0$  mg/dL [1.78 – 1.94 mmol/L] and  $> 6.0$  mg/dL [1.94 mmol/L]). For eligible patients who are not taking phosphate binder(s) at screening visit, serum phosphorus at V1 will be used for stratification. For eligible patients who are taking phosphate binder(s) at screening visit, serum phosphorus at V1a will be used for stratification.
- Assessment of the primary efficacy (change from baseline in serum phosphorus level) endpoint is at Week 8.
- Wash out period is only for patients on phosphate binder(s) at screening. Patients not on phosphate binder(s) would proceed directly to the start of the 8-week treatment period (Day 1).
- During the Treatment Period, patients return to the investigative site every 2 weeks. Samples for laboratory measurements are collected at each site visit. After the results are received from the central laboratory, the serum phosphorus results are evaluated. Investigator will be informed by the IVRS/IWRS for dose titration. If the serum phosphorus is  $\geq 4.6$  mg/dL ( $\geq 1.49$  mmol/L), the patient is to be instructed by the investigator to increase their study treatment dose by 1 tablet TID with meals. If the serum phosphorus is  $< 2.7$  mg/dL ( $< 0.87$  mmol/L), the patient is to be instructed by the investigator to decrease their study treatment dose by 1 tablet TID with meals.

## 1.5 MODIFICATIONS TO THE STATISTICAL SECTION OF THE PROTOCOL

There are no major changes to the protocol statistical section.

The first patient was screened on 7 Jun 2016. The first patient was randomized on 21 July 2016.  
There are no planned interim analyses.

## **1.6 STATISTICAL MODIFICATIONS MADE IN THE STATISTICAL ANALYSIS PLAN**

Not applicable.

## 2 STATISTICAL AND ANALYTICAL PROCEDURES

### 2.1 ANALYSIS ENDPOINTS

#### 2.1.1 Demographic and baseline characteristics

The baseline value is defined as the last available value obtained up to the date and time of the first double-blind investigational medicinal product (IMP) administration. For patients randomized and not treated, the baseline value is defined as the last available value obtained up to the date and time of randomization.

All baseline safety and efficacy parameters (apart from those listed below) are presented along with summary statistics in the safety and efficacy sections ([Section 2.4.4](#) and [Section 2.4.5](#)).

#### *Demographic characteristics*

Demographics and baseline characteristics will be listed and summarized by treatment group and overall for randomized patients. Standard descriptive statistics will be presented for the following continuous variables:

- age (years)
- weight (kg);
- height (cm);
- body mass index [BMI] (kg/m^2) [calculated as (weight/height) where weight is in kg and height is in m];

The total counts and percentages of patients will be presented for the categorical variables of:

- age group (years) : <45, ≥45 to <65, ≥65 to <75, and ≥75 years; and <65, and ≥65 years.
- gender (Male, Female);
- race (Asian, other).
- Alcohol use within 12 months.

#### *Disease characteristics at baseline*

Disease characteristics at baseline will be listed and summarized by treatment group and overall for randomized patients. Standard descriptive statistics will be presented for eGFR and total counts and percentages of patient will be presented for the CKD stage at baseline.

#### *Medical and Renal history*

Medical and renal history findings at Screening will be tabulated overall and by treatment group for randomized patients, including any past and/or concomitant diseases or past surgeries, primary cause of chronic kidney disease (CKD) and parathyroid gland resection.

## 2.1.2 Prior or concomitant medications

As specified in the protocol, all medications and therapies taken by the patient from 30 days prior to the signing of the informed consent through the end of the study will be recorded.

Medications will be coded to anatomic therapeutic class (ATC) term and generic name using the World Health Organization (WHO) Drug dictionary using the latest version at the date of DBL. Tables will be sorted first by alphabetical ATC and then by descending frequency of generic name within ATC based on the prevalence across all treatment groups. The highest ATC level for each medication will be used for summary. Multiple records of the same drug (based on generic name) used by a patient are counted once within a drug class and within a generic name.

Prior medications will be summarized, both overall and by treatment group for the Safety Set, by ATC and generic name for all medications.

Prior medications are defined as follows:

- Prior medications include any medications that were used within 30 days of screening visit and prior to the date of first dose of study drug.

Concomitant medications will be summarized by treatment group for the Safety Set, by ATC and generic name for all medications.

Concomitant medications are defined as follows:

- Concomitant medications include any medications used between study drug start and end of study.

Any technical details related to computation, dates, imputation for missing dates are described in [Section 2.5](#).

## 2.1.3 Efficacy endpoints

### 2.1.3.1 Primary efficacy endpoint(s)

The primary endpoint is the change from baseline in serum phosphorus level at Week 8.

The baseline of serum phosphorus value will be the last serum phosphorus level obtained before the first double-blind IMP dosing.

The serum phosphorus at Week 8 will be the serum phosphorus level obtained within the Week 8 analysis window.

All serum phosphorus values (scheduled or unscheduled) may be used to provide a value for the primary endpoint if appropriate according to above definition. The analysis window used to allocate a time point to a measurement is defined in [Section 2.5.3](#).

### **2.1.3.2 Secondary efficacy endpoint(s)**

The secondary efficacy endpoints are:

- The change from baseline in total cholesterol at Week 8
- The change from baseline in LDL-C at Week 8
- The change from baseline in calcium-phosphorus product at Week 8
- The change from baseline in iPTH level at Week 8
- Percentage of patients reaching the target serum phosphorus level (4.6 mg/dL [1.49 mmol/L], inclusive) at Week 8
- The change from baseline in serum phosphorus level at Week 4.

### **2.1.4 Safety endpoints**

The safety analysis will be based on the reported adverse events (AEs) and other safety information, such as clinical laboratory data and vital signs.

#### ***Observation period***

The observation of safety data will be as follows:

- Pre-treatment period: The pre-treatment observation period is defined from the signed informed consent up to the first dose of double-blind IMP.
- Treatment Emergent Adverse Event (TEAE) period: The TEAE observation period is defined as the time from the first dose of double-blind IMP to the last dose of double-blind IMP+3 days.
- Post-treatment period: The post-treatment observation period is defined as the time starting the day after the end of the TEAE period up to the end of the study (see definition in Protocol Section 6.2.1).

#### **2.1.4.1 Adverse events variables**

All adverse events (including serious adverse events [SAE], and AEs of special interest) will be coded to a lower-level term (LLT), preferred term (PT), high-level term (HLT), high-level group term (HLGT), and associated primary system organ class (SOC) using the version of Medical Dictionary for Regulatory Activities (MedDRA) currently in effect at Sanofi at the time of database lock.

Record the occurrence of adverse events (including serious adverse events and AEs of special interest) from the time of signed informed consent until the end of the study.

#### ***Adverse event observation period***

Pre-treatment adverse events are adverse events that developed or worsened or became serious from the signed informed consent date up to first administration of the IMP.

Treatment-emergent adverse events (TEAE) are adverse events that developed or worsened or became serious during the treatment period.

Post-treatment adverse events are adverse events that developed or worsened or became serious during the post-treatment period

### ***Serious adverse event***

A **serious adverse event** (SAE) is any untoward medical occurrence that:

- Results in death, or
- Is life-threatening, or

Note: The term “life-threatening” in the definition of “serious” refers to an event in which the patient was at risk of death at the time of the event; it does not refer to an event which hypothetically might have caused death if it were more severe.

- Requires inpatient hospitalization or prolongation of existing hospitalization, or
- Results in persistent or significant disability/incapacity, or
- Is a congenital anomaly/birth defect
- Is a medically important event

### ***Adverse event of special interest***

An AESI is an AE (serious or non-serious) of scientific and medical concern specific to the Sponsor’s product or program, for which ongoing monitoring and immediate notification by the Investigator to the Sponsor is required. Such events may require further investigation in order to characterize and understand them.

- Pregnancy of a female subject entered in a study as well as pregnancy occurring in a female partner of a male subject entered in a study with IMP
  - Pregnancy occurring in a female patient entered in the clinical trial or in a female partner of a male patient entered in the clinical trial. It will be qualified as an SAE only if it fulfills one of the seriousness criteria
  - In the event of pregnancy in a female participant, IMP should be discontinued.
  - Follow-up of the pregnancy in a female participant or in a female partner of a male participant is mandatory until the outcome has been determined.
- Symptomatic overdose (serious or non-serious) with IMP/NIMP
  - An overdose (accidental or intentional) with the IMP/NIMP is an event suspected by the Investigator or spontaneously notified by the patient (not based on systematic pills count). Renvela is a non-absorbed drug, thus it is not possible to define a symptomatic overdose prospectively. However, the investigator may use his or her judgment to report an event that he or she considers to be a symptomatic overdose using the corresponding screens in the e-CRF using the Term “Symptomatic OVERDOSE (accidental [or intentional])”. The patient should be monitored and appropriate symptomatic treatment instituted. The circumstances of the overdose should be clearly

specified in the verbatim. Of note, asymptomatic overdose has to be reported as a standard AE.

- Increase in alanine transaminase (ALT) (see the “Increase in ALT” flow chart in Appendix A of the protocol).

#### **2.1.4.2 Deaths**

The deaths observation period are defined as below.

- Death on-study: deaths occurring during the on-study observation period (defined as the time from start of treatment until the end of the study)
- Death on-treatment: deaths occurring during the treatment-emergent adverse event period

#### **2.1.4.3 Laboratory safety variables**

The clinical laboratory data consist of hematology (complete blood count [CBC], differential, platelet and prothrombin time), chemistry (serum phosphorus, calcium [adjusted for albumin], albumin, calcium-phosphorus product, chloride, bicarbonate, uric acid, sodium, potassium, glucose, blood urea nitrogen [BUN], alanine aminotransferase [ALT], aspartate aminotransferase [AST], creatinine), and lipid panel (total cholesterol, LDL-C, high-density lipoprotein cholesterol [HDL-C], non-high-density lipoprotein cholesterol [non-HDL-C] and triglycerides). Laboratory variables which are defined as efficacy variables will not be included in the safety analysis.

Clinical laboratory values after conversion will be analyzed into standard international units and international units will be used in all listings and tables.

Blood samples for clinical laboratories will be taken at Visit 1 (Week -4), Visit 2 (Week 0), Visit 3 (Week 2), Visit 4 (Week 4), Visit 5 (Week 6), Visit 6 (Week 8) and/or early termination unless otherwise specified.

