9.3.2 Laboratory safety variables

The clinical laboratory data consist of hematology (complete blood count [CBC], differential, platelet and prothrombin time), chemistry (serum phosphorus, calcium [adjusted for albumin], albumin, calcium-phosphorus product, chloride, bicarbonate, uric acid, sodium, potassium, glucose, blood urea nitrogen [BUN], alanine aminotransferase [ALT], aspartate aminotransferase [AST], creatinine), and lipid panel (total cholesterol, LDL-C, high-density lipoprotein cholesterol [HDL-C], non-high-density lipoprotein cholesterol [non-HDL-C] and triglycerides).

Clinical laboratory values will be analyzed after conversion into standard international units. International units will be used in all listings and tables.

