11.4.3.2 Laboratory data and vital signs

The summary statistics of all laboratory variables, all vital signs parameters will be calculated for each visit, and last value assessed during the treatment period and presented by treatment group.

The incidence of PCSAs at any time during the TEAE period (on-treatment PCSAs) will be summarized by treatment group whatever the baseline level and/or according to the following baseline categories:

- Normal/missing
- Abnormal according to PCSA criterion or criteria

For laboratory parameters for which PCSA criterion is not defined, similar table(s) using the normal range could be provided.

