##### ***General common rules***

All safety analyses will be performed on the safety population as defined in [Section 2.3.2](#), unless otherwise specified, using the following common rules:

- Safety data in patients who do not belong to the safety population (eg, exposed but not randomized) will be listed separately.
- The baseline value is defined as last available value obtained up to the date and time of the first double-blind IMP administration, except other specified.
- The potentially clinically significant abnormality (PCSA) values are defined as abnormal values considered medically important by the Sponsor according to predefined criteria/thresholds based on literature review and defined by the Sponsor for clinical laboratory tests, vital signs, and ECG (see 0). In case the threshold defined in the PCSA list for a given lab parameter is below the ULN, the following PCSA criterion will be used for the PCSA analysis:  $>\text{PCSA threshold}$  or  $>\text{ULN}$  (if  $\text{ULN} \geq \text{PCSA threshold}$ ).
- PCSA criteria will determine which patients had at least 1 PCSA during the treatment-emergent adverse event period, taking into account all evaluations performed during the treatment-emergent adverse event period, including nonscheduled or repeated evaluations. The number of all such patients will be the numerator for the on-treatment PCSA percentage.
- The treatment-emergent PCSA denominator by group for a given parameter will be based on the number of patients assessed for that given parameter in the treatment-emergent adverse event period by treatment group on the safety population.

All measurements, scheduled or unscheduled, will be assigned to analysis windows defined in [Section 2.5.3](#), Table 2 in order to provide an assessment for Week 2 to Week 8 time points.

- For quantitative safety parameters based on central laboratory/reading measurements, descriptive statistics will be used to summarize results and change from baseline values by visit and treatment group. Summaries will also be provided for the last on-treatment value. The last on-treatment value is defined as the value collected at the same day/time of the last administration of IMP. If this value is missing, this endpoint value will be the closest value prior to the last dose intake.

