#### **2.4.5.3 Analyses of laboratory variables**

The summary statistics (including number, mean, median, standard deviation, minimum and maximum) of all laboratory variables (central laboratory values and changes from baseline) will be calculated for each visit or study assessment (baseline, each post baseline time point, last on-treatment) by treatment group. This section will be organized by biological function as specified in [Section 2.1.4.3](#).

The incidence of PCSAs (list provided in 0) at any time during the treatment-emergent adverse event period will be summarized by biological function and treatment group whatever the baseline level and/or according to the following baseline status categories:

- Normal/missing
- Abnormal according to PCSA criterion

For parameters for which no PCSA criteria are defined, similar table(s) using the normal range will be provided.

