**Table 1 - Analysis windows definition**

Time point	Targeted study day	Analysis window in study days
Week 2	15	2 to 22
Week 4	29	23 to 36
Week 6	43	37 to 50
Week 8	57	51 to 64
Follow-up	71	65 ~

For the case multiple visit dates fall into the same analysis window, the one close to the targeted study day is applied. In case of two visit dates are equally close to targeted date, the original record of visit will be applied. For the Week 8, the analysis visit should use the one close to the last IMP dose intake.

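### SAP 2.1.4.3 drops four protocol-listed analytes from the laboratory safety analysis without declaring it, and the abnormality counts that go with them are not replaced elsewhere

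*SAP*

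**What the plan says.** Protocol 9.3.2 defines the laboratory safety variables with no exception. The chemistry list begins "chemistry (serum phosphorus, calcium [adjusted for albumin], albumin, calcium-phosphorus product, chloride, bicarbonate, uric acid" and runs on to creatinine; the lipid panel includes total cholesterol and LDL-C. Protocol 11.4.3.2 then makes three statements. First, "The summary statistics of all laboratory variables, all vital signs parameters will be calculated for each visit". Second, the by-arm incidence of on-treatment PCSAs will be summarised. Third, "For laboratory parameters for which PCSA criterion is not defined, similar table(s) using the normal range could be provided".

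SAP 2.1.4.3 gives the same list and adds: "Laboratory variables which are defined as efficacy variables will not be included in the safety analysis". SAP 2.4.5.3 plans by-arm summaries at baseline, at each later time point and for the last on-treatment value, then PCSA incidence, and then: "For parameters for which no PCSA criteria are defined, similar table(s) using the normal range will be provided". It also says "This section will be organized by biological function as specified in" section 2.1.4.3, the section that holds the exclusion. Under the general common rules of SAP 2.4.5, PCSA patients are counted "taking into account all evaluations performed during the treatment-emergent adverse event period, including nonscheduled or repeated evaluations".

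On the efficacy side, SAP 2.4.4.2 plans by-arm descriptive statistics, including minimum and maximum, on the mITT population. The note to SAP Table 1 reduces repeat measurements to one: "For the case multiple visit dates fall into the same analysis window, the one close to the targeted study day is applied".

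SAP 1.5 reports no major change to the protocol's statistical section. SAP 1.6 reports none made in the SAP.

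**The concern.** The SAP narrows a safety analysis that the protocol states without exception, and a reader who relies on SAP 1.5 and 1.6 would not know. Clinically significant laboratory changes are a protocol safety endpoint (section 9.3). For a drug whose intended action is to lower phosphorus, the natural laboratory question is how many patients in each arm went below normal on treatment. With the exclusion in force, no planned output gives that count, and one PCSA count that the protocol commits to disappears as well.

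**Working it through.** The plan states no figure on this point, so the check is a cross-match of lists followed by a search for replacement output.

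**1. Which analytes are removed.** Protocol 9.3.2 has 14 chemistry analytes and 5 lipid analytes: 14 + 5 = 19. The laboratory efficacy variables in SAP 2.1.3 are phosphorus, total cholesterol, LDL-C, calcium-phosphorus product and iPTH. iPTH is not on the safety list, so the overlap is four: 4/19 = 21%.

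**2. Which table each would have had.** SAP Appendix A has a criterion for total cholesterol (7.74 mmol/L or more) and none for the other three. So 1 of 4 falls under the PCSA table and 3 of 4 under the normal-range rule of SAP 2.4.5.3.

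| Analyte | Appendix A criterion | Incidence table lost | Status in protocol 11.4.3.2 |
|---|---|---|---|
| Total cholesterol | yes | PCSA count | firm |
| Phosphorus | no | normal-range table | optional |
| Calcium-phosphorus product | no | normal-range table | optional |
| LDL-C | no | normal-range table | optional |

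The Safety-population summaries of the last on-treatment value are lost for all four.

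**3. Does other output replace them?**

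- *Efficacy descriptives (SAP 2.4.4.2).* These give location, spread and extremes by arm, but no count beyond a limit. Read literally, they cover secondary variables, so phosphorus enters only through its Week 4 endpoint, and possibly as a change rather than a level. SAP 2.1.1 and 2.4.1 soften that reading, because they promise baseline efficacy summaries and quartiles for baseline phosphorus.
- *Windows (SAP Table 1).* There are four on-treatment windows (Weeks 2, 4, 6 and 8), each keeping one value per patient. Protocol 10.1 asks for an immediate recheck of clinically relevant abnormal results, so two values in one window are foreseeable, and a low one can drop out of the reported minimum. By-visit safety summaries use the same windows; only an any-time incidence table avoids this.
- *Titration counts (SAP 2.4.3.1).* These cover the Renvela group only. Titration follows Visits 3, 4 and 5, that is 3 of the 4 on-treatment phosphorus visits, so a low Week 8 value is missed and there is no placebo comparison.
- *Adverse event tables.* Protocol 10.4.2 makes a laboratory abnormality recordable if, among other conditions, it leads to a dose modification. This route is by arm but conditional, and the dose-modification condition again arises through titration only after Visits 3 to 5.
- *LOCF Week 8 values.* These approximate the last on-treatment value, but in the mITT population and without abnormality counts.

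None of these gives an any-time, by-arm count for any of the four analytes.

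**4. Would restoring SAP 2.4.5.3 be enough?** Not fully. It does not say that low and high values are separated. Patients enter with phosphorus of at least 5.5 mg/dL. If the laboratory's upper limit lies below that (the documents do not give it), a combined out-of-range count could consist mainly of high values and hide the low ones.

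**The case against.** Reporting efficacy analytes in the efficacy section is an explicit, pre-specified choice that avoids duplication. The mITT population holds nearly every treated patient with a post-baseline phosphorus value, so most of the distributional content is moved rather than lost. SAP 1.5 denies only major changes. Appendix A looks like a general list, since it also covers ECG and other parameters that this trial does not schedule, so its cholesterol row says little about intent. All of this stands, and it keeps the point minor. It does not supply the missing counts, and the protocol's PCSA commitment does not depend on what Appendix A was meant for.

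A reader might infer more than the documents support:

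- *That the protocol promises a phosphorus normal-range table.* It makes that table optional. The firm wording is the SAP's own, in a section that refers back to the list with the exclusion, so the conflict inside the SAP is soft. The firm protocol table that is lost is the total cholesterol PCSA count.
- *That the phosphorus count is the only thing lost.* Step 2 of the working shows that it is not.
- *That low phosphorus would go unseen.* Minima, adverse event recording and Renvela down-titrations each show part of it.
- *That a count below normal is the protocol's safety endpoint itself.* Clinical significance is tabulated through PCSA criteria, and phosphorus has none.

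**Conclusion.** The mismatch is real and undeclared: four listed analytes leave the safety analysis against protocol 9.3.2 and 11.4.3.2. What is not replaced is one PCSA count (total cholesterol), three normal-range tables (phosphorus, calcium-phosphorus product, LDL-C) and the Safety-population last-on-treatment summaries for all four. The below-normal phosphorus count matters most for safety, but its omission departs from the SAP's own rule for parameters without a criterion more than from a firm protocol commitment.

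This assumes that the exclusion sentence is followed as written. The documents give neither the laboratory's normal limits nor an expected rate of low phosphorus, so no number of affected patients is claimed. The titration mark of 2.7 mg/dL is not stated to be the lower normal limit. This is a reporting gap: the primary test, error control, responder definition and data collection are unaffected. Severity is minor.

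**What to change.** 1. Delete the exclusion sentence in SAP 2.1.4.3, so that SAP 2.4.5.3 applies to all four analytes in the Safety population.
2. State in SAP 2.4.5.3 that the normal-range tables count patients with below-range and above-range values separately, by arm, over all on-treatment evaluations including unscheduled and repeat ones.
3. If any analyte stays excluded, declare that departure in SAP 1.5. Exempting phosphorus alone would still leave the total cholesterol PCSA count missing.

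The cost is one deleted sentence, one added sentence and routine tables from data already collected, with no new visits or samples. The downside is some duplication between efficacy and safety tables, which a cross-reference can handle.
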